2.1.2 SipNose Utility, Reliability, and Safety

The SipNose device was specifically designed to facilitate drug loading and user experience particularly suited for the purposes of this trial.

2.1.2.1 Utility

The SipNose device consists of a nose piece, compressed air chamber, activation lock to prevent unwanted activation, and activation button (Figure 2: SipNose Device Components- SP1N1C1). The device also consists of a cover that prevents the device being activated accidentally.

[figure not shown]

Figure 2: SipNose Device Components- SP1N1C1

The drug is kept within its original commercial bottle or primary container until use and stored under the required conditions as stated in the original drug label. Prior to administration, the drug is drawn out from the primary container using a commercial syringe, and transferred into the Device Nose Piece that serves as a secondary drug container for a short period of time (several minutes). The drug contacts only with the device parts that are made of polypropylene (PP), medical grade USP Class VI compliant. PP is an acceptable material for short term exposure of drugs, including insulin³⁸. For example, this material has been used in the following products: MONOJECT SoftPack; GLUCOPRO Insulin Syringe; BD Insulin Syringes, all commonly utilized syringes in clinical settings.

The nostrils come in contact only with the nose piece which is made of the same PP mentioned above. The parts that come in contact with intact skin (subject's hands) are made of PET-G Tritan™ – Estman MX711 (details in sections 3 and 4 of Investigator's brochure).

Drug stability studies have not been conducted for this study as insulin has been shown to be stable at refrigeration and room temperature conditions for up to 31 days [39; Section 16.2 –package insert).

2.1.2.2 Reliability

The SipNose device has demonstrated an ability to reliably reproduce the same spray dose volume consistency. The U.S. Food & Drug Administration (FDA) guidance recommends a consistency of ≤ 1 spray outside 80 – 120% and 0 sprays outside 75 – 125% dose volume. During tests with insulin, SipNose devices expelled an average volume of 105.14ul (Range: 99.6-112ul), all individual spray volumes were within the range of 93%-107% of the target volume 100ul, and mean spray volume was within 95%-105% of the target volume of 100ul. Therefore, both individual and mean results meet the FDA guidelines (See Compatibility Testing document – for details).

Studies have shown that the SipNose device consistently targets the upper nasal cavity, thus delivering the dispelled agent to the region critical for CNS delivery. When using a human nasal model cast, the SipNose more reliably targeted the upper nasal cavity (see section 5.1 in IB) as compared to other commercial devices (LMA MAD NasalTM). In a preclinical rat model, 11C-choline was reliably delivered to the olfactory epithelium and into the brain immediately following administration (detected in brain ~3min following administration). PET-CT scan were measured from ~3 min following administration up to 1 hour. An example of the scan at 40-45 minutes after drug administration is shown in the IB. (See section 5.2 in IB). In addition, midazolam brain concentrations using the intranasal SipNose device were comparable to that obtained with IV administration in a rat model, although blood levels were lower than the IV administration (see section 11 in Investigator’s brochure). The SipNose device demonstrated higher anterior and posterior brain concentrations of insulin following IN delivery as compared to IV administration (see section 11.8 in Investigator’s brochure).

In a human study using SPECT-CT analysis, it was found that the volume of drug deposition effectively targeted the upper/middle posterior region of the nasal cavity with negligible lung deposition (see section 5.3 in Investigator’s brochure). Another human study involving patients presenting with epileptic seizures treated with IN midazolam using the SipNose device showed that the treatment improved electrographic seizures and was well-tolerated in this population (See section 11.4 in Investigator’s brochure). Finally, delivery of IN midazolam anesthesia with the SipNose device resulted in a higher level of sedation in patients undergoing a surgical procedure compared to IN drug delivery with a commercial delivery device (see section 11.4 from Investigator’s brochure).

2.1.2.3 Safety

SipNose device is an aerosol nasal delivery platform that uses pressurized delivery through the discharge of compressed air. The pressure used in the SipNose is similar to that used in commercial nasal inhalers and is up to 6 bars (1 bar=14.5 Psi). Impact force of the SipNose device is in the range of 1.5-6.5 grams, and is comparable to that found in commercialized inhalers, dry powder inhalers and other nasal delivery devices in the field ⁴⁰ The actual impact force that is detected following aerosol release via the SipNose device, is found to be 2-5gr, and specifically with 100ul of the drug Insulin is 2.7 ± 0.3 gr.

Safety experiments performed have shown no evidence of irritation or local tissue damage following treatment with the SipNose nasal delivery device in both humans and animals (see section 11 in Investigator’s brochure).

2.2 Continuous Glucose Monitor (CGM) device

The commercially available Dexcom G6 CGM system (Figure 3) measures the glucose level in the interstitial fluid under the skin. The CGM system includes a sensor which has a small wire that is inserted under the skin, a transmitter that attaches to the sensor and a smartphone app that collects and displays the glucose results. The sensor will be placed under the skin and can stay in place for up to 10 days. The sensor will measure the glucose level in the interstitial fluid every five minutes and transmit that data to the smartphone. The screen will show in real-time the participant’s glucose value, most recent glucose trends, and an arrow indicating which way the glucose trend is predicted to go. Alarms can

be set to alert the participant to glucoses that are too high or too low, or if glucose trends are changing quickly. The data collected by the system can be downloaded and evaluated for several CGM-based metrics.

Figure 3: Dexcom G6 CGM System

3 Objectives

3.1 Primary Objective

Demonstrate no significant increase in dangerous hypoglycemia with administration of intranasal insulin in T1D participants with intact awareness of hypoglycemia.

3.2 Secondary Objectives

1. Describe changes in overall glycemic control with administration of intranasal insulin in T1D participants with intact awareness of hypoglycemia
2. Describe changes in hypoglycemia awareness with administration of intranasal insulin in T1D participants with intact awareness of hypoglycemia
3. Describe changes in safety endpoints with administration of intranasal insulin in T1D participants with intact awareness of hypoglycemia

3.3 Exploratory Objective

Describe changes in memory, attention and executive function with administration of intranasal insulin in T1D participants with intact awareness of hypoglycemia.

4 Endpoint(s)

4.1 Primary Endpoints

Dangerous hypoglycemia defined by percent time below range (<54 mg/dL) from real-time continuous glucose monitoring (CGM).

4.2 Secondary Endpoints

- Overall metrics and glycemic control from real-time CGM data during each treatment period defined as:
 - Percent time in range (70-180 mg/dL) from real-time CGM
 - Percent time below range (<70 mg/dL) from real-time CGM
 - Percent time above range (>180 mg/dL and >250 mg/dL) from real-time CGM
 - Mean glucose from real-time CGM
 - Coefficient of variation (%CV) from real-time CGM
 - Glucose management indicator (GMI) from real-time CGM
 - Percent time of active sensor wear from real-time CGM
- Hypoglycemia awareness measured three ways using:

- 3 hypoglycemia unawareness questionnaires/scores (Gold Score, Clarke survey, HypoA-Q)
- Time from CGM reading of, <70 mg/dL, 54-<70 mg/dL and <54 mg/dL to time of participant hypoglycemia awareness obtained from participant journals
- Glucose value from real-time CGM at onset time of hypoglycemia awareness obtained from participant journals
- Safety outcomes include:
 - Adverse events
 - Neuropathy test changes
 - Review of patient non-research insulin doses and medications
 - HbA1c
 - EKG
 - Smell test changes
 - C-SSRS assessment

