1.1 Background/Rationale

Hypoglycemia, or the fear of it, is one of the most significant limits to current management of type 1 diabetes (T1D). Consequences of hypoglycemia, both physical and cognitive, can be severe and in some cases fatal.^{1,2} Unfortunately, hypoglycemia occurs with high frequency among patients with T1D. Occurrence estimates put the frequency of mild hypoglycemia at 1 to 2 events per patient per week and severe hypoglycemia (requiring assistance from another person) at 0.2 to 3.2 events per patient per year.¹ Data from the T1D Exchange Clinic Registry (77 clinics in 35 states collecting common data on children and adults with T1D), has shown 18.6% of patients with T1D for ≥ 40 years have had 1 or more severe hypoglycemia episodes (resulting in seizure or loss of consciousness) within the last year.³ With repeated episodes of hypoglycemia, the counter-regulatory pathways to restore normal glucose are blunted, and patients can become unaware of the hypoglycemia. It is estimated that 40% of patients with T1D have hypoglycemia unawareness.⁴ Patients with long-standing T1D, intensive therapy at advanced age, and frequent hypoglycemia are at the highest risk for hypoglycemia unawareness.^{5,6}

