Guidelines suggest treating older patients with T1D and those with longer duration of disease with less aggressive HbA1c targets, with the assumption that this will help reduce the risk of hypoglycemia.⁷ Despite these more conservative glycemic targets, they do not appear to protect patients from severe hypoglycemia.³ Indeed, even those patients with T1D who think they can tell when they are hypoglycemic are still at risk for hypoglycemia. Taking patients ≥ 60 years old who have had T1D ≥ 20 years, and comparing those who have had at least 1 severe hypoglycemia episode in the last year to a case-control group with no severe hypoglycemia in the last 3 years, it was shown that those with severe hypoglycemia had more glucose variability ($P = 0.008$) and had continuous glucose monitoring (CGM) levels < 60 mg/dL for ≥ 20 min on 46% of days compared with 33% of days in control subjects ($P = 0.10$). This was despite there being no appreciable difference in HbA1c levels.⁶ It is also of note that the group with perceived “awareness” to hypoglycemia had surprisingly high numbers of hypoglycemic episodes. In T1D patients ≥ 60 years old, time spent in hypoglycemia (< 70 mg/dL) was highest in younger patients, those with shorter diabetes duration, and lower HbA1c levels, and was strongly correlated to glycemic variability based on CGM.⁸

The use of CGM technology can reduce the frequency of hypoglycemia and allows for more aggressive insulin titration to lower HbA1c without increasing hypoglycemia events.⁹⁻¹¹ Indeed, higher HbA1c goals may help reduce the amount of time in hypoglycemia for patients with longer duration of T1D, however higher HbA1c targets are not enough to prevent severe hypoglycemia.⁸ The use of CGM, however, does not reliably restore hypoglycemia awareness.¹¹ Advancements in insulin pump therapy and CGM using hybrid closed-loop artificial pancreas systems holds promise as well for better glycemic control without severe hypoglycemia.¹² Despite these benefits, only 15-20% of patients with T1D use CGM with insulin injections or insulin pump therapy.¹³

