5.4 CGM Device and Training

CGM device and smartphone app training will occur at the start of both treatment periods, and user guide materials will be provided. Participants will first download the Dexcom G6 Mobile app to their smartphone. After entering their transmitter's serial number into the app, there is a 2 hour warm-up for the CGM. Next they will identify a location on their abdomen as directed by study staff for insertion of the sensor. After cleaning the skin, participants are instructed how to use the applicator to insert the sensor and connect the transmitter to the sensor. After the 2 hour warm up is over, the CGM will start transmitting real-time glucose data. Participants will be allowed to use CGM data for their diabetes management. Blood glucose monitoring can be performed using the participant's own glucose meters if CGM readings do not match a participant's symptoms. CGM alert thresholds will be set at default levels of 70 mg/dL for low glucose, and 180 mg/dL for high glucose. These alerts can be adjusted during the study as needed. The G6 app also has a feature where wearers can mark events such as food or exercise; for the purposes of this study, participants will be instructed to use the "other" activity as a marker of symptomatic hypoglycemia (which they can use as an alternative to the hard-copy participant journal for documentation of symptomatic hypoglycemia)

[figure not shown]

Figure 13: Inserting the CGM Sensor

The Dexcom G6 system allows for the wearer to share their glucose data with up to 5 followers remotely through the Follow app. This "sharing" feature will be downloaded and started with assistance of the study staff. The study staff, including the PI, will have 24 hour access to this data for safety purposes, if participants call with any concerns during the study. A CLARITY mobile account will be set up for participants (using the CLARITY app which links to the G6 Mobile app) and linked to the research site, which can capture device data for analysis.

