5.6 Study Duration

Study participation will last approximately 10 weeks, consisting of a screening visit, 4 study phase visits, 1 follow-up safety assessment visit and at least 5 phone call visits. Subjects will receive treatment with IN insulin for a period of 14-20 days. Subjects who discontinue treatment will continue to complete follow-up measures as possible.

6 Study Population

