6.1 Eligibility Criteria

6.1.1 Inclusion Criteria

- Adult patients (age ≥ 18) with type 1 diabetes diagnosis and a duration of diabetes of at least 10 years
- Gold score < 4
- HbA1c $\geq 6.5\%$ within the last 3 months or at screen visit
- Stable insulin regimen (MDI or insulin pump) for at least 3 months, as deemed stable by principal investigator
- Depression/anxiety medications stable for at least 3 months
- Ability and willingness to wear CGM continuously during study participation
- Participants must use their own smartphone, and have the ability and willingness to use CGM smartphone applications compatible with their smartphone
- Ability and willingness to check SMBG using own supplies, as instructed by study staff
- Ability and willingness to document when having symptoms of hypoglycemia in the CGM smartphone app or in a diary
- If using insulin pump, willing to operate insulin pump without threshold suspend feature or hybrid closed-loop, if applicable
- Proficient in speaking, reading and understanding English in order to complete surveys and testing of cognitive function
- Women of child-bearing age must agree to procure and use contraception throughout the study

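### Two of the three awareness measures exist only for lows the participant recorded, so a worsening of awareness can be understated; report the share of CGM lows with a symptom entry beside them

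*Combined protocol and SAP*

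**What the plan says.** The second secondary objective (section 3.2) is to "Describe changes in hypoglycemia awareness with administration of intranasal insulin in T1D participants with intact awareness of hypoglycemia". Section 4.2 serves it with three questionnaires (Gold, Clarke, HypoA-Q) and two event-based measures. The first is a delay: "Time from CGM reading of, <70 mg/dL, 54-<70 mg/dL and <54 mg/dL to time of participant hypoglycemia awareness obtained from participant journals". The second is the sensor reading when the participant becomes aware, worded in the plan as "Glucose value from real-time CGM at onset time of hypoglycemia awareness obtained from participant journals".

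Both event-based measures take the awareness time from the participant. Eligibility (section 6.1.1) requires "Ability and willingness to document when having symptoms of hypoglycemia in the CGM smartphone app or in a diary". Section 5.4 offers an app marker, "which they can use as an alternative to the hard-copy participant journal for documentation of symptomatic hypoglycemia". Training at Visits 2 and 7 likewise concerns logging the onset of symptoms.

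No section defines a CGM hypoglycemic event or says what happens to a CGM low with no entry. Three places come close:

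- Section 12.1 assumes data are missing at random and excludes subjects. That is a subject-level rule and does not address unmatched events within a subject.
- Section 12.3 asks for suitable summary statistics, without inference.
- Section 11.6.1 says the analysis will capture non-severe hypoglycemia, but does not link it to symptom entries.

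**The concern.** A low that passes unnoticed is the clearest sign of reduced awareness. Under the plan it has no awareness time and no glucose at awareness, so it leaves both summaries instead of lengthening the first or lowering the second. If awareness worsened on one treatment, more of the slow or unnoticed lows would disappear from that treatment's figures, and the change would look smaller than it was.

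Selecting participants with a Gold score below 4 does not rule this out. Section 1.1 itself warns that "even those patients with T1D who think they can tell when they are hypoglycemic are still at risk for hypoglycemia". Without the number of lows that had no entry, a reader cannot tell a stable awareness time from one that looks stable because the slow lows are absent.

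The clock start is also undefined. A participant may log symptoms at 60 mg/dL and then fall to 48. The entry precedes the reading below 54, and the plan does not say whether the time to awareness is then negative, zero or excluded.

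**Working it through.** **What the documents supply.** They give no awareness delay, episode length or recording rate, and no planned figure for these measures, so there is nothing to reproduce. The calculations below use assumed inputs and show direction and range only. They ignore the low-glucose alert.

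**Time to awareness.** Assume the delay is exponential with mean m, the episode lasts c minutes, and an entry is made only if symptoms come before the episode ends.

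- Share recorded: P = 1 − exp(−c/m)
- Mean among recorded episodes: E = m − c·exp(−c/m)/P
- Part of a true doubling (m to 2m) that is kept: (E at 2m − E at m)/m

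Example with c = 45 and the mean going from 10 to 20 minutes:

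- m = 10: exp(−4.5) = 0.011, P = 0.989, E = 9.49
- m = 20: exp(−2.25) = 0.105, P = 0.895, E = 14.70
- Kept: (14.70 − 9.49)/10 = 52%, while the share recorded falls from 99% to 90%

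The same calculation across the assumed range:

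| Mean delay (min) | c = 30 | c = 45 | c = 60 | c = 90 |
|---|---|---|---|---|
| 5 to 10 | 70% | 90% | 97% | 100% |
| 10 to 20 | 30% | 52% | 70% | 90% |
| 20 to 40 | 9% | 18% | 30% | 52% |
| 30 to 60 | 4% | 9% | 15% | 30% |

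**A worsening can vanish.** At c = 45, assume 60% of episodes have mean delay 20 and 40% have mean 60. Doubling the slow group raises the true mean from 0.6×20 + 0.4×60 = 36 to 0.6×20 + 0.4×120 = 60 minutes. The recorded mean goes from 16.1 to 15.9, while the share recorded falls from 75% to 66%.

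**Different assumptions, same direction.** With a log-normal delay (log-SD 0.8) and 30-minute episodes, a true median change from 10 to 20 minutes appears as 9.2 to 14.6.

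**Glucose at awareness.** Assume symptom thresholds with SD 6 mg/dL, capped at 70, and lowest glucose around 60 (SD 7, below 70). Moving the threshold mean from 65 to 60 changes the true mean glucose at awareness from 64.3 to 59.9 (−4.4). The recorded mean goes from 65.9 to 62.9 (−3.0), and the share from 76% to 54%.

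**Random loss.** If 30% of entries are lost for unrelated reasons, with no cut-off at the episode's end, simulation recovers the mean delay unchanged.

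**Matching window.** Assume symptoms begin at a mean of 60 mg/dL (SD 4 to 6) and glucose falls to 48. Then 98% to 99.9% of events have an entry before the low point; counting only entries between 48 and 70 gives 93% to 99%. Only 7% to 14% have an entry made below 54. The window therefore decides what the <54 class shows.

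**Number of events.** Section 1.1 says: "Occurrence estimates put the frequency of mild hypoglycemia at 1 to 2 events per patient per week". Section 5.6 says: "Subjects will receive treatment with IN insulin for a period of 14-20 days". For 10 participants:

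- 10 × 1 × 14/7 = 20, to 10 × 2 × 20/7 = 57 events per treatment. The rate is not stated to be CGM-detected.
- Section 1.1 also gives a CGM rate: below 60 mg/dL for at least 20 minutes on 33% of days in controls aged 60 or over. That is 10 × 14 × 0.33 = 46, to 10 × 20 × 0.33 = 66 person-days. It leaves out lows between 60 and 70 and repeats within a day, and may not carry over to this population.

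**The case against.** The strongest reply is that the attenuation is assumed, not shown. A range of 4% to 100% depends wholly on chosen delays and episode lengths. Participants are selected for intact awareness, and if delays are 5 to 10 minutes and episodes last 45 minutes or more, 90% or more of a doubling is kept. Nothing in the documents supports the 30-to-60-minute rows or the mixture. This stands: the calculations establish direction and possibility only.

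The model also leaves out the low alert (default 70 mg/dL, adjustable) and the permission to use CGM data for management (section 5.4). An alert may prompt an entry, or lead to treatment that ends the episode. This stands too, and it limits both the model and the proposed proportion.

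A reader might infer that the recorded share reveals how biased the mean is. It does not. At 45 minutes, a share of 78% fits a 30-minute mean delay with complete logging. It fits equally well a 5-minute delay with 22% of entries forgotten, where the mean is sound.

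Finally, the plan works at logging: diary training is reinforced by phone at Visits 3, 4, 8 and 9, and the diary is reviewed at Visits 5 and 10. The questionnaires need no recorded episode. Both points soften the concern, but neither gives the number of unrecorded lows by treatment.

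**Conclusion.** The point holds as a minor one. Both event-based awareness measures are conditional on a participant entry, and the plan neither counts nor handles CGM lows without one. If unnoticed lows go unrecorded, both summaries can understate a worsening. The size cannot be derived from the documents. Under the assumptions shown, the effect on mean time ranges from negligible to almost complete loss of the signal, and it is small when delays are short relative to episodes.

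The documents do not support the stronger reading that the awareness results will be biased. That requires non-recording to depend on awareness, which is plausible but not established. Nor does the concern reach the primary endpoint, its power or the other CGM time-in-range measures: these come from CGM without any participant entry.

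**What to change.** In sections 4.2 and 12.3, before results are seen:

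1. Define a CGM hypoglycemic event as one continuous descent below 70 mg/dL, with a pre-specified minimum duration and separation, classed by its lowest level (54 to <70, or <54).
2. For each treatment, report the number of events and the proportion with a symptom entry (journal or app marker) in a pre-specified window. The window opens before the threshold crossing and closes at recovery. An entry earlier in the same descent counts for the <54 class. Give this per participant and pooled.
3. Show the time and glucose-at-awareness summaries beside that proportion, labelled as conditional on recorded episodes, and state how entries before the clock start are handled.
4. State that a missing entry may mean a noticed low that was not logged, and that alerts may prompt entries. Read the proportion with the diary review at Visits 5 and 10, and describe alert settings by period where available.

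The cost is wording and slightly more analysis of data already collected. No change to alerts or treatment is proposed. The downside is that the unrecorded share may overstate unawareness. With 10 participants it will be imprecise, and one or two people could dominate a pooled figure, hence the per-participant summary.
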